12. HEALTH OUTCOMES ANALYSES

12.1. Endpoint / Variables

12.1.1. Main Study

- Preference between injections of LA HIV treatment and daily oral HIV treatment at Week 48
- Preference between LA injection every 8 weeks and LA injection every 4 weeks at Week 48 (Q8W arm only)
- Change from baseline in total “treatment satisfaction” score, and individual item scores of the HIV Treatment Satisfaction Status Questionnaire (HIVTSQs) at Weeks 24, 48 and 152
- Change from baseline in life satisfaction, HIV medication, and disclosure worries using HIV/AIDS Targeted Quality of Life (HAT-QoL) at Weeks 24 and 48
- Change in treatment satisfaction over time using the HIV Treatment Satisfaction Change (HIVTSQc) questionnaire at Week 48
- Change from Week 8 in Dimension Scores and individual item scores assessing pain during injection, anxiety before and after injection, willingness to be injected in the future and overall satisfaction with mode of administration over time using Perception of Injection (PIN) questionnaire at Weeks 24, 48 and 152
- Change from baseline in treatment acceptance using ACCEPT at Weeks 24, 48 and 152
- Reasons for continuation of receiving injectable HIV treatment at Baseline (Day 1) visit. This is an exploratory endpoint.
- Reasons for switching to injectable HIV treatment at Baseline (Day 1) visit. This is an exploratory endpoint.
- Preference for CAB LA + RPV LA injection compared to daily oral for participants receiving oral bridging during the Maintenance and/or Extension phases at Week 152. This is an exploratory endpoint.

12.1.2. Sub-study

- Change from gluteal to thigh in total “treatment satisfaction” score, and individual item scores of the HIV Treatment Satisfaction Status Questionnaire (HIVTSQs) during the Thigh Injection phase as well as the change from thigh to gluteal during the Return to Gluteal Injection phase
- Change from gluteal to thigh using the HIV Treatment Satisfaction Change (HIVTSQc) questionnaire at Sub-study Week 16
- Changes in the tolerability of injections (NRS) over time during the sub-study
- Preference for thigh injections compared with prior gluteal injections and the injections received during the Return to Gluteal Injection phase respectively.

12.2. Summary Measure

For main study, mean treatment difference (Q8W – Q4W) at visits of interest, except for Preference between LA injection every 8 weeks and LA injection every 4 weeks at Week 48.

For sub-study, mean difference between thigh injections and gluteal injections from visits of interest, except for the Preference between thigh injections and gluteal injections.

12.3. Population of Interest

The health outcomes analyses will mainly be based on the Intent-to-Treat Exposed population, unless otherwise specified.

Analysis of Reason for continuation will be based on a subset of the Intent-to-Treat Exposed population who were randomized to Q4W arm in ATLAS (i.e. ATLAS Q4W population).

12.4. Analysis of Reason for switch will be based on a subset of Intent-to-Treat Exposed population who either were randomized to SOC arm in ATLAS or did not participate in ATLAS study (i.e. SOC population).Strategy for Intercurrent (Post-Randomization) Events

If a participant discontinues treatment prior to the timepoint of interest such that there is no evaluable assessment for the timepoint of interest, the data will be computed or imputed (see Section 15.6.6).

12.5. Statistical Analyses / Methods

Details of the planned displays are provided in [Appendix 15](#): List of Data Displays and will be based on GSK Data Standards and statistical principles.

Unless otherwise specified, endpoints / variables defined in Section 12.1 will be summarised using descriptive statistics, graphically presented (where appropriate) and listed.

12.5.1. Statistical Methodology Specification

| Statistical Analyses |
|--|
| Endpoints |
| 
 • Change from Baseline in 
 ○ HIVTSQs total treatment satisfaction score at Weeks 24,48 and 152 ○ ACCEPT general acceptance score at Weeks 24, 48 and 152 ○ HAT-QoL (Life satisfaction, HIV medications, disclosure worries) at Weeks 24 and 48 • Change from Week 8 in PIN Domain Scores (Bother of ISRs, Leg movement, Sleep, and Acceptance) and Individual Items Scores (Anxiety before, Pain, Satisfaction, Anxiety After, Willingness) at Weeks 24, 48 and 152 |

| Statistical Analyses | |
|---|--|
| Model Specification | |
| 
 The analysis for HIVTSQs, ACCEPT and HAT-QoL will be performed for subjects with and without prior exposure to CAB+RPV separately. 
 For subjects without prior exposure to CAB+RPV, an analysis of covariance (ANCOVA) model will be used at each visit during the maintenance phase with covariates: treatment, age (<50, ≥ 50 years old), sex at birth, race (i.e. white, non-white) and baseline score value for other endpoints (as a continuous variable). For subjects with prior exposure to CAB+RPV, an analysis of covariance (ANCOVA) model will be used at each visit during the maintenance phase with covariates: treatment, age (<50, ≥ 50 years old), prior exposure to CAB+RPV (i.e. 1 to 24 weeks, >24 weeks), sex at birth, race (i.e. white, non-white) and baseline score value (as a continuous variable). For PIN, an analysis of covariance (ANCOVA) model will be used at each visit during the maintenance phase with covariates: treatment, age (<50, ≥ 50 years old), prior exposure to CAB+RPV (i.e. 0 weeks, 1 to 24 weeks, >24 weeks), sex at birth, race (i.e. white, non-white), and Week 8 score value (as a continuous variable). Adjusted point estimates will be derived as LSMEANS using the observed margins (OM) option within PROC MIXED in SAS. The superiority testing of Q8W compared to Q4W with respect to change from baseline in HIVTSQs total score at Week 48 will be performed using the fixed sequence procedure to control for the type I error rate at the nominal level of 5%. If the superiority testing within subjects without prior exposure to CAB+RPV demonstrates Q8W is superior to Q4W in change from baseline in HIVTSQs total score at Week 48 at two-sided 5% level of significance, the superiority testing at the same level of significance (i.e. two-sided 5%) within subjects with prior exposure to CAB+RPV will be followed. No adjustment for multiplicity will be applied for other tests as they will be considered supportive. Interactions between treatment and each of the covariates will not be assessed unless the exploratory subgroup analyses on the primary endpoint highlights significant interactions. In this situation, the interaction(s) of interest will be assessed and, if necessary, results will be reported in the clinical study report. Interactions between treatment and the baseline score will be investigated but not included in the model. If interactions are found to be significant ($p < 0.10$), results may be presented separately by subgroup. | |
| Dataset | |
| 
 LOCF dataset will be used. | |
| Model Results Presentation | |
| 
 Adjusted treatment difference (Q8W – Q4W), its 95% CI and the associated p-value. The interaction between treatment and the baseline score will be included in a footnote. Plots of adjusted mean change from baseline (95% CI) for each treatment group, and the adjusted mean difference (95%CI) between the two treatment arms from the model will be generated across visit. | |

| Statistical Analyses | |
|--|--|
| HIVTSQc | |
| 
 Total Treatment Satisfaction Score (Change) at Week 48 | |

| |
|--|
| Model Specification |
| 
 • An analysis of variance (ANOVA) model will be used with covariates: treatment, age (<50, \geq 50 years old), prior exposure to CAB+RPV (i.e. 0 weeks, 1 to 24 weeks, $>$24 weeks), sex at birth and race (i.e. white, non-white). • Adjusted point estimates will be derived as LSMEANS using the observed margins (OM) option within PROC MIXED in SAS. • Interactions between treatment and each of the covariates will not be assessed unless the exploratory subgroup analyses on the primary endpoint highlights significant interactions. In this situation, the interaction(s) of interest will be assessed and, if necessary, results will be reported in the clinical study report. If interactions are found to be significant ($p<0.10$), results may be presented separately by subgroup. • No adjustment for multiplicity will be applied as these analyses will be considered supportive. |
| Dataset |
| The observed case (OC) dataset uses only the data that is available at Week 48, with no imputation for missing values. |
| Model Results Presentation |
| Adjusted means, 95% CI, and associated p-value will be presented for the treatment difference (Q8W – Q4W). |

| |
|---|
| Statistical Analyses |
| PIN/HIVTSQs |
| 
 • Change from Week 8 in the PIN acceptance score at Week 24, Week 48 and Week 152 • Change from Sub-study Baseline in the HIVTSQs total treatment satisfaction score at Sub-study Week 16, Sub-study Week 24 (for Q8W arm) or Sub-study Week 20 (for Q4W arm). |
| Statistical Test |
| 
 • The Wilcoxon Signed-Rank Test will be used to evaluate: 
For PIN, whether the change from Week 8 to each post Week 8 main study visit, is statistically different from zero based on a two-sided $p<0.05$.
 
For HIVTSQs, whether the change from Sub-study Baseline to each post-baseline sub-study visit is statistically different from zero based on a two-sided $p<0.05$.
 |
| Dataset |
| 
 • For PIN, LOCF dataset will be used. • For HIVTSQs, observed dataset will be used. |
| Results Presentation |
| 
 • For PIN, summary statistics at each timepoint (Week 8, Week 24, Week 48 and Week 152) and p-value for each comparison between scores at Week 24/48/152 with scores at Week 8. • For HIVTSQs, summary statistics at Sub-study Baseline, Sub-study Week 16, Sub-study Week 24 (for Q8W arm) or Sub-study Week 20 (for Q4W arm), and p-value for the comparison between scores at each post-baseline sub-study visit with scores at Sub-study Baseline. |

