15.3.4. Assessment Window for Health Outcome Data

15.3.4.1. PIN / HAT-QoL / HIVTSQs / HIVTSQc / ACCEPT / Preference in Main Study

PIN, HAT-QoL, HIVTSQs, HIVTSQc, ACCEPT, Preference, reasons for oral bridging and preference questionnaire assessments will be assigned to analysis visits as follows:

1. Baseline will be defined as last available recorded value up to and including the Maintenance treatment start date (expected to be collected at Day 1). Baseline is not applicable for PIN, HIVTSQc and Preference assessments.
2. For post-baseline visits, if the nominal visit identifier as captured in the source dataset corresponds to a scheduled collection per the Time and Events Schedule (see Section 15.2 and Table 15) and the assessment is collected in the Maintenance or Extension Phase (per Table 18), then the nominal visit identifier will be kept as the analysis visit.
3. For post-baseline visits, if the nominal visit identifier is unscheduled or withdrawal, then the following procedure will be used:
 - a) Assign the assessment to a study phase according to Table 18. Proceed to step b if the assessment is assigned to the Maintenance or Extension Phase.
 - b) Identify the 'last nominal visit' with the HO assessment performed prior to the unscheduled/withdrawal visit to be slotted in the same phase.
 - c) The unscheduled/withdrawal visit will be slotted to the planned nominal visit subsequent to the 'last nominal visit' in the same phase. If the 'last nominal visits' does not exist (e.g. no records originate from a planned nominal visit), then the unscheduled/withdrawal visit will be slotted to the first planned nominal visit after Day 1 in the same phase. If the planned nominal visit subsequent to the 'last nominal visit' is not available, then the unscheduled/withdrawal visit will be slotted to the last planned nominal visit after Day 1 in the same phase.

Example 1, for HATQoL, the planned nominal visits are Day 1, Week 24, and 48. If a participant has the 'last nominal visit' (with HATQoL assessment) at Week 24 prior to withdrawal at Week 36, the withdrawal assessment will be slotted to the subsequent planned nominal visit of Week 48.

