Example 2, for HATQoL, if there is unscheduled visit between Week 24 and Week 48. This unscheduled visit will be slotted to Week 48 per the rule. In this case, there are two assessments with analysis visit equal to Week 48 (i.e. the slotted value and the value at original nominal week 48 visit). The original nominal value will be selected for summary per the rule below for multiple records—see Section 15.3.5.1.

Table 15 Planned Nominal Visit of Health Outcome Data in Main Study

| Questionnaire | Day 1 | Week 8 | Week 24 | Week 48 | Week 152 |
|--|---|--------|---------|---------|----------|
| PIN | | X | X | X | X |
| HAT-QoL | X | | X | X | |
| HIVTSQs | X | | X | X | X |
| HIVTSQc | | | | X | |
| ACCEPT | X | | X | X | X |
| Preference | | | | X | |
| Reasons for Oral Bridging and Preference | | | | | X |
| NOTES: | Day 1 visits are recorded as "Baseline" visits in the database. | | | | |

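### The Week 48 HIVTSQc model carries no starting-score covariate although a Day 1 HIVTSQs total is scheduled for everyone: a cheap efficiency gain of unknown size

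*SAP*

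**What the plan says.** The endpoint in SAP Section 12.5.1 is "Total Treatment Satisfaction Score (Change) at Week 48". The model is specified thus: "An analysis of variance (ANOVA) model will be used with covariates: treatment, age" (under or over 50 years), three-level prior exposure to CAB+RPV, sex at birth and race. It uses observed cases, and the section calls the comparison supportive, with no multiplicity adjustment. The display list in Section 15.15.5.10 runs it twice, for participants from the ATLAS Q4W arm (Table 6.29) and for those from SOC (Table 6.30).

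The other questionnaire models in Section 12.5.1 all contain a starting score:

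- HIVTSQs, ACCEPT and HAT-QoL, participants with prior exposure: "race (i.e. white, non-white) and baseline score value (as a continuous variable".
- The same endpoints, participants without prior exposure: "baseline score value for other endpoints (as a continuous variable". The wording is untidy, but a baseline term is there.
- PIN: the Week 8 score, since PIN is not given at Day 1.

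Section 15.3.4.1 defines baseline for the questionnaires as the "last available recorded value up to and including the Maintenance treatment start date (expected to be collected at Day 1". It then adds: "Baseline is not applicable for PIN, HIVTSQc and Preference assessments". Table 15 in that section, "Planned Nominal Visit of Health Outcome Data in Main Study", schedules HIVTSQs at Day 1 and HIVTSQc only at Week 48.

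**The concern.** HIVTSQc asks participants to rate how their satisfaction has changed. How satisfied they were at the start is a natural candidate to explain some of the spread in those ratings, and the trial schedules that measurement on the companion status form before treatment begins. Section 15.6.6 builds both totals from items 1 to 11 of the paired forms, so an association is plausible. The plan adjusts for a starting score everywhere else and leaves it out here without giving a reason specific to the status score.

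At stake is the width of the confidence interval for one secondary, supportive comparison, and the correction of any chance imbalance between arms in Day 1 satisfaction. No error-controlled test depends on it.

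**Working it through.** **No plan figure to reproduce.** The SAP gives no sample size, power, standard deviation, effect size or correlation for HIVTSQc. The planned total of about 1020 (510 per arm, Section 1) was set on the virologic non-inferiority margin.

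**Inputs.** From the SAP: 510 per arm, 1:1 allocation, and the covariates listed above. Assumed: r, the partial correlation of Day 1 HIVTSQs with Week 48 HIVTSQc given the covariates already in the model. It is shown over a range that includes zero.

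**Formulas.** In a randomised linear model, adding one baseline covariate multiplies the variance of the treatment difference by about 1 − r². The interval width is multiplied by √(1 − r²). The equivalent increase in sample size is 1/(1 − r²) − 1. With 510 per arm the unadjusted 95% half-width is 1.96 × √(2/510) = 0.123 SD. Power that would be 80% unadjusted (two-sided 5%) becomes Φ[(1.96 + 0.842)/√(1 − r²) − 1.96].

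| Assumed r | Variance ratio | Interval width ratio | Equivalent extra participants | Half-width (SD) | 80% power becomes |
|---|---|---|---|---|---|
| 0 | 1.00 | 1.000 | 0% | 0.123 | 80.0% |
| 0.1 | 0.99 | 0.995 | 1.0% | 0.122 | 80.4% |
| 0.3 | 0.91 | 0.954 | 9.9% | 0.117 | 83.6% |
| 0.5 | 0.75 | 0.866 | 33.3% | 0.106 | 89.9% |

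The half-widths take all 1020 participants in one model. Tables 6.29 and 6.30 each use only part of them, so the actual intervals will be wider, but the ratios are essentially unchanged.

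**Check.** Simulating 2,000 trials of 510 per arm with three strata gave variance ratios of 1.00, 0.89 and 0.72 at r = 0, 0.3 and 0.5, against 1.00, 0.91 and 0.75 from the formula. That is close enough for this purpose.

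**Missing Day 1 scores.** If a share m of participants were dropped for lacking a Day 1 score, the variance would be multiplied by (1 − r²)/(1 − m). The gain is cancelled when m = r²: at 1%, 9% and 25% missing for r = 0.1, 0.3 and 0.5. Section 5.2 leaves a missing baseline missing, so adding the covariate without a rule could remove the benefit.

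**The case against.** The strongest reply is that nothing here is wrong. The comparison is randomised and stratified, the planned ANOVA is unbiased, and a change questionnaire has no baseline of its own. The satisfaction test that carries weight is the change in HIVTSQs at Week 48, which sits in the controlled sequence of Section 5.5.2 and is already baseline-adjusted. All of this stands, and it confines the point to efficiency. The statement that baseline is not applicable means only that HIVTSQc is not administered at Day 1. It is no reason to leave out the status score.

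A second reply is that prior exposure, already in the model, may absorb the relation. This is why r is defined as a partial correlation. In Table 6.29 the term should absorb nothing: ATLAS participants had to reach ATLAS Week 52 before randomisation (Section 15.2.1, note a), and exposure is counted from the start of oral CAB in ATLAS (Section 15.6.2), so those from the ATLAS Q4W arm should all fall in the over-24-weeks stratum.

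A third reply concerns timing. Section 5.4.2 shows that this SAP version postdates the Week 48 data cut, and Tables 6.29 and 6.30 are Week 48 deliverables only. Replacing the planned model now would be a post hoc change in an open-label trial. This stands and shapes the remedy.

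A reader might also infer more than the SAP supports:

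- That precision is known to be lost. It is not: r is undocumented and could be near zero.
- That the Day 1 HIVTSQs score is used throughout the satisfaction models. It enters only the HIVTSQs ANCOVA; the other questionnaires use their own starting scores.
- That Day 1 HIVTSQs measures satisfaction with exactly the treatment that HIVTSQc takes as its reference. The questionnaire text is redacted and, for ATLAS participants, the version follows the original ATLAS arm (Section 15.2.1, note v), so this cannot be confirmed for everyone. A pre-treatment covariate remains a legitimate adjustment regardless.

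**Conclusion.** The point holds as a low-cost efficiency improvement, not as an error. The HIVTSQc comparison is the one modelled questionnaire score without a continuous starting-score covariate, while a suitable Day 1 measurement is scheduled and already used in the companion model. The gain is a proportional fall of about r² in the variance of the treatment difference: nil at r = 0, 1% at 0.1, 9% at 0.3 and 25% at 0.5. These values of r are assumptions. The conclusion also rests on an approximately linear relation and on retaining participants whose Day 1 score is missing. The downside is one degree of freedom per model. The planned estimate remains unbiased, and no controlled conclusion changes.

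**What to change.** In the HIVTSQc part of Section 12.5.1, add the Day 1 HIVTSQs total score as a continuous covariate, which turns the ANOVA into an ANCOVA, and apply it in the models behind both Table 6.29 and Table 6.30. State that a missing Day 1 score is set to the overall mean, pooled across arms, of that table's analysis set, as an exception to Section 5.2. Because the filled-in value does not depend on arm, it does not bias the randomised comparison, and no observed Week 48 value is lost.

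Where the Week 48 analysis has already been run, keep the planned ANOVA as reported and show the adjusted model beside those two tables as a labelled sensitivity analysis.

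The cost is one model term, one missing-value rule and a rerun of two tables. No new data or participants are needed.

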| 
 To assess viral resistance in participants experiencing protocol-defined confirmed virologic failure. To assess patient reported outcomes during the thigh injection phase by administering the following health outcome measurements: Numerical Rating Scale (NRS) and HIVTSQ. | 
 Incidence of treatment emergent genotypic and phenotypic resistance to CAB, RPV during the thigh injection phase. Numerical Rating Scale (NRS): To assess the tolerability of injections during both the Thigh and Gluteal Injection Phase HIVTSQ (both s and c versions): To measure levels of satisfaction and detect change in satisfaction when switching from gluteal to thigh injections in total “treatment satisfaction” score, and individual item scores of the HIV Treatment Satisfaction Questionnaire (HIVTSQ) during the Thigh Injection Phase as well as the change from thigh during the Return to Gluteal Phase. |
| 
 To assess participant's preference of thigh injections during the thigh injection phase compared to gluteal injections. | 
 Preference Questionnaire: To assess patient's preference, and reasons for preference, for injections received during the Thigh Injection Phase compared with prior gluteal injections as well as for injections received during the Return to Gluteal phase compared with prior thigh injections. |
| Exploratory Objectives | Exploratory Endpoints |
| 
 To assess additional safety events including other AEs, SAEs, and safety labs of monthly and every two months dosing of CAB LA and RPV LA following intramuscular injections in the vastus lateral (thigh) muscle in HIV-1 infected participants currently enrolled in the A2M sub-study. | 
 Incidence of other AEs not of special interest, SAEs and change in laboratory and change in laboratory parameters from the last gluteal injection (prior to the Thigh Injection Phase). |

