15.15.7.8. Health Outcomes Tables

| Health Outcomes Tables | | | | | |
|---|--------------------|-------------------------|--|---|-------------|
| No. | Population | IDSL / Example Shell | Title | Programming Notes | Deliverable |
| HIV Treatment Satisfaction Questionnaire Status or Change Version (HIVTSQs, HIVTSQc) | | | | | |
| 6.1 | Sub-study ITT-E | 207966/primary_34/T6.7 | Proportion of Subjects with HIVTSQs - Individual Item Scores by Visit in Sub-study | | Sub-study |
| 6.2 | Sub-study ITT-E | 207966/primary_34/T6.9 | Summary of HIVTSQs - Total Treatment Satisfaction Score by Visit in Sub-study | Add a column "P Value [1]" to the right of the Column "Max." Add the footnote: [1] Sub-study Week 16, Sub-study Week 24 (for Q8W arm) or 20 (for Q4W arm) are compared with the Sub-study Baseline using Wilcoxon signed-rank test." | Sub-study |
| 6.3 | Sub-study ITT-E | 207966/primary_34/T6.11 | Summary of HIVTSQs - Change in Total Treatment Satisfaction Score in Sub-study | Remove the column 'Prior Exposure to CAB+RPV (weeks)'. Replace "Act. Rel. Time" With "Change", the new "Change" column includes "Change from Baseline to Week 16" for both arms, "Change from Baseline to Week 20" for Q4W and "Change from Baseline to Week 24" for Q8W, "Change from Week 16 to Week 20" for Q4W arm and "Change from Week 16 to Week 20" for Q8W. Remove the footnote. | Sub-study |
| 6.4 | Sub-study ITT-E | 207966/primary_34/T6.13 | Summary of HIVTSQs - Change in Individual Item Score in Sub-study | Similar notes to above. | Sub-study |

| Health Outcomes Tables | | | | | |
|---------------------------------|--------------------|-------------------------|---|-------------------|-------------|
| No. | Population | IDSL / Example Shell | Title | Programming Notes | Deliverable |
| 6.5 | Sub-study ITT-E | 207966/primary_02/T6.23 | Proportion of Subjects with HIVTSQc - Individual Item Change Score at Sub-study Week 16 (Thigh Injection Phase) | | Sub-study |
| 6.6 | Sub-study ITT-E | 207966/primary_02/T6.27 | Summary of HIVTSQc - Individual Item Change Score at Sub-study Week 16 (Thigh Injection Phase) | | Sub-study |
| 6.7 | Sub-study ITT-E | 207966/primary_02/T6.25 | Summary of HIVTSQc - Total Treatment Satisfaction Change Score at Sub-study Week 16 (Thigh Injection Phase) | | Sub-study |
| Tolerability of Injection (NRS) | | | | | |
| 6.8 | Sub-study ITT-E | Shell HO_T3 | Proportion of Subjects with Each Tolerability of Injection (NRS) Score by Visit in Sub-study | | Sub-study |

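### At the sub-study return visit the only HIVTSQs test compares gluteal with gluteal; the stated thigh-to-gluteal change is only described, and its Q8W row names a visit that arm does not have

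*SAP*

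**What the plan says.** Section 12.1.2 gives the sub-study HIVTSQs endpoint two parts: the change from gluteal to thigh, "as well as the change from thigh to gluteal during the Return to Gluteal Injection phase". The objectives table in Section 2.2.1 has the same second part, "as well as the change from thigh during the Return to Gluteal Phase", and lists it ahead of the exploratory endpoints. Section 12.2 sets the sub-study summary measure as the "mean difference between thigh injections and gluteal injections from visits of interest".

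Section 12.5.1 defines the tested variable as "Change from Sub-study Baseline in the HIVTSQs total treatment satisfaction score at Sub-study Week 16" and at Week 24 (Q8W) or Week 20 (Q4W). The rule, a two-sided signed-rank test at 0.05 on observed data, reads "For HIVTSQs, whether the change from Sub-study Baseline to each post-baseline sub-study visit is statistically different from zero", and the result to be presented is the "p-value for the comparison between scores at each post-baseline sub-study visit with scores at Sub-study Baseline". The note to Table 6.2 (Section 15.15.7.8) agrees: Week 16 and the return visit "are compared with the Sub-study Baseline using Wilcoxon signed-rank test".

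Tables 6.3 (total score) and 6.4 (item scores) list changes between visits, including a row from Week 16 to the return visit. No p-value is specified for either table.

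**The concern.** For the return phase, the reference visit in the test is not the reference visit in the endpoint. The endpoint asks what happens to satisfaction when a participant goes from thigh back to gluteal, so the reference has to be Week 16. The test uses Sub-study Baseline, which precedes any experience of thigh injection. The SAP decided to attach a p-value to the return visit, and that p-value belongs to a different question. It will nevertheless sit in the return-visit row of Table 6.2, where a hurried reader may take it as the result for the return-phase endpoint.

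The plan does use the right logic elsewhere. For the injection-pain scale, Table 6.10 takes the return-phase change from the last thigh visits (Weeks 12 and 13 for Q4W, Weeks 8 and 9 for Q8W).

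**Working it through.** The SAP gives no power or sample-size figure for this comparison, so there is none to reproduce. The check is to map each HIVTSQs visit to its injection site and compare the contrasts.

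**Step 1: which injection site each score reflects.**

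| Score | Q4W | Q8W | Site | Source |
|---|---|---|---|---|
| B, Sub-study Baseline | Day 1 | Day 1 | gluteal | 15.3.4.3: last value up to the first thigh injection date; 15.2.3 and 15.2.4: questionnaires other than NRS come at the start of the visit |
| T | Week 16 | Week 16 | thigh | 15.3.4.3: visits up to Week 16 are Thigh Injection phase |
| R, return visit | Week 20 | Week 24 | gluteal | 15.2.3, 15.2.4 and 15.3.4.3 |

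If the Day 1 score is missing, an earlier main-study value may serve as B; that is also on gluteal injections. HIVTSQc cannot fill the gap, because it is scheduled only at Week 16.

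**Step 2: endpoint against test.**

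| Contrast | Meaning | Endpoint? | Tested? |
|---|---|---|---|
| T − B | thigh − gluteal | yes, first part | yes |
| R − T | gluteal − thigh | yes, second part | no; described in Tables 6.3 and 6.4 |
| R − B | gluteal − gluteal | no | yes |

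**Step 3: what R − B measures.** Let the mean score be g on gluteal injections and g + d on thigh injections, and let a fraction f of the shift reverse on return. Then

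- T − B = d
- R − T = −f·d
- R − B = (1 − f)·d

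With f = 1, R − B = 0 while the endpoint change is −d. With f = 0, R − B = d while the endpoint change is 0. With f = 0.5 the two are equal in size and opposite in sign. R − B measures what remains of the shift; R − T measures what changed on return. The mean of R − T can be worked out as (R − B) − (T − B) when the same participants contribute, but its p-value cannot be read off the two planned p-values.

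**Step 4: illustration.** Input from the SAP: 41 per arm (Section 2.3, approximately 82 in all) and a two-sided 0.05 signed-rank test. Assumed, not in the SAP: normal scores, independent visit noise, d in units of the SD of a change, full reversal (f = 1), every participant with all three scores. 3,000 simulated trials gave these rejection rates:

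| d | T vs B (planned) | R vs B (planned) | R vs T (stated endpoint) |
|---|---|---|---|
| 0 | 5.7% | 4.5% | 5.6% |
| 0.3 | 43.5% | 5.0% | 43.7% |
| 0.5 | 86.2% | 4.7% | 86.0% |
| 0.7 | 99.2% | 5.1% | 98.8% |

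The flat 5% for R vs B follows from setting f = 1. It shows that the two tests answer different questions; it is not a forecast for this sub-study.

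**Step 5: the descriptive row.** For changes from Baseline, the note to Table 6.3 correctly gives Week 20 for Q4W and Week 24 for Q8W. For changes from Week 16 it gives Week 20 for both arms. The Q8W schedule in Section 15.2.4 goes from Week 17 to Week 24, with no Week 20 visit. Taken literally, the Q8W row cannot be produced. Table 6.4 inherits the label because its note refers back to Table 6.3.

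**The case against.** The strongest reply is that the contrast has been planned. Section 12.5 makes description the default for the endpoints in 12.1, Section 12.1.2 promises a change and not a test, and Tables 6.3 and 6.4 carry it. Other sub-study patient-reported outcomes (pain scale, HIVTSQc, preference) have no test either. R versus B is also a legitimate question: did satisfaction return to its level before thigh injections? The Table 6.2 note names its comparator, and the Week 16 score appears in the same table with its own thigh-versus-gluteal test.

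Most of this stands, and it rules out two stronger readings. A reader might infer that the thigh-to-gluteal endpoint has been dropped; it has not, because it is described. A reader might also infer that the return-visit p-value is null by construction, or will lead to a conclusion opposite to the truth. The first is so only if reversal is assumed complete. The second requires ignoring the footnote, the adjacent Week 16 row and Table 6.3.

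The reply does not explain why the one return-phase comparison chosen for testing is the one that is not an endpoint. Nor does the descriptive fallback work for Q8W as labelled.

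**Conclusion.** The concern holds in limited form. The only inferential test at the return visit does not match the stated return-phase endpoint or the thigh-versus-gluteal summary measure, and the row that does describe that endpoint is mislabelled for Q8W. This rests on the SAP's own schedules and definitions and needs no assumed figure.

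The size is modest. It concerns one supportive analysis in each sub-study arm; no decision rule in the SAP depends on it; the gluteal-to-thigh half of the endpoint is properly tested at Week 16; and the main-study primary analysis is unaffected. The rejection rates above should not be quoted as power lost by the plan: effect size, SD of change and full reversal are assumptions, and the number of paired observed scores may fall below 41. It should be corrected because the correction is almost free.

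**What to change.** - **Section 12.5.1:** make the return-phase analysis a signed-rank test of the within-participant change in HIVTSQs total score from Sub-study Week 16 to Week 20 (Q4W) or Week 24 (Q8W). Keep Sub-study Baseline as the reference for Week 16. If the return visit is still tested against Baseline, label that test *return to pre-thigh level*.
- **Table 6.2:** bring the footnote into line with that labelling.
- **Table 6.3:** put the new p-value on the row for the change from Week 16 to the return visit, and make the Q8W label end at Week 24.
- **Table 6.4:** correct the same Q8W label, and state that the p-value applies to the total score only, since this table takes its notes from Table 6.3.

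The cost is a sentence or two in 12.5.1 and edits to three table notes. All scores are already scheduled. The one statistical drawback is an additional supportive p-value in each arm if the Baseline comparison is kept.
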